10.15 Mobile Health Data handling

Data downloaded from the Mobile Health platform (MHP) such has number of morning and evening sprays administered, NRS scales, number of spasm counts, C-SSRS questionnaire, MSSS-88 questionnaire have specific information to link the date MHP data were submitted to the date the data are referring to which have to be reported in SDTM and ADAM as detailed in Table . In practice, any time the variable XGRID contains the term “Late” the date to be used refers to the day before the one coming from MHP.

Table 10.15-1 MHP data - Date Handling

XPGRID	Explanation
Initial on time Diary	Served from 6:00pm to 11:59 pm to the day a participant is moved to screening
Initial late Diary	Served from 12:00 am to 03:05 pm the next morning when the initial On Time Diary was NOT completed the previous day
On time diary	Served from 6:00pm to 11:59 pm when the Initial On Time, On time, or Missed On Time Diary was completed the previous day
Late diary	Served from 12:00 am to 03:05 pm when On Time Diary was NOT completed the previous day
Missed on time	Served from 6:00pm to 11:59 pm when an Initial Late, or Missed Late Diary was served on the same day
Missed late	Served from 12:00 am to 03:05 pm when the Missed On Time Diary was Not completed the previous day

10.16 Modified Ashworth Scale (MAS) Transformed Score

The MAS will be conducted and scored on 10 lower limb muscle groups (hip flexors and adductors, knee flexors and extensors, and plantar flexors) on the left and the right side of the body at Screening, Day 1 H0, D1H3 and D21 each treatment period.

For the purpose of the analysis, the result of each of the 10 MAS scores will be transformed using the following algorithm: MAS untransformed [to MAS transformed] scores; 0[0], 1[1], 1+[2], 2[3], 3[4] and 4[5].

Each MAS transformed score is ranging from ‘0’ (No increase in muscle tone) to ‘5’ (Affected part rigid in flexion or extension).

These scores will then be used to derive 3 mean Lower Limb Muscle Tone (LLMT) measures at D1H0, D1H3 and D21 of each treatment period.

- The LLMT-6: defined as the average of the 6 individual MAS transformed scores of knee flexors, knee extensors, and plantar flexors on both sides of the body. For any given patient, at a given visit, the LLMT-6 will be set to missing if individual MAS transformed scores are missing for 3 or more of the 6 specified muscle groups (as described in [Table 10.16-1](#)),
- The LLMT-10: defined as the average of the 10 individual MAS transformed scores of knee flexors, knee extensors, plantar flexors, hip flexors and hip adductors on both sides of the body. For any given patient, at a given visit, the LLMT-10 will be set to missing if individual MAS transformed scores are missing for 5 or more of the 10 specified muscle groups (as described in [Table 10.16-1](#)),
- The LLMT-4 defined as the average of the 4 individual MAS transformed scores of knee flexors, knee extensors on both sides of the body. For any given patient, at a given visit, the LLMT-4 will be set to missing if individual MAS transformed scores are missing for 2 or more of the 4 specified muscle groups (as described in [Table 10.16-1](#)).

In addition, LLMT-6/LLMT-4/LLMT-10 scores derived with individual MAS transformed score missing in at least one muscle group will be identified.

Table 10.16-1 Lower Limb Muscle Tone - Missing Data Handling

Parameter	Number of items (muscle groups) included in score derivation	Minimum number of muscle group scores required for score derivation (at least 50%)
LLMT-4	4	3
LLMT-6	6	4
LLMT-10	10	6

LLMT-4 = Lower Limb Muscle Tone-4; LLMT-6 = Lower Limb Muscle Tone-6; LLMT-10 = Lower Limb Muscle Tone-10.

The change and percentage change from baseline will then be calculated (as respectively described in [Section 10.3](#) and in [Section 10.4](#)) for each LLMT score.

The percentage change from baseline values will also be categorized as $\leq -20\%$, $\leq -30\%$, $\leq -40\%$ and $\leq -50\%$ to assess an improvement of respectively $\geq 20\%$, $\geq 30\%$, $\geq 40\%$ and $\geq 50\%$

Although unlikely to occur as per inclusion criteria 6.1.5, if a baseline LLMT score is equal to 0, the percentage change from baseline will be imputed using the following formula:

- Percentage change from baseline $= (x+1)*100$, where x is the post baseline value .

Missing LLMT scores will be considered as not having met any of the improvement criteria (imputed as failure).

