6.1 Inclusion Criteria

Screening (Visit 1)

For inclusion in the trial, patients must fulfill ALL of the following criteria:

- 6.1.1 Male or female, aged 18 years or above.
- 6.1.2 Willing and able to give informed consent for participation in the trial (see [Section 15.2](#)).
- 6.1.3 Willing and able (in the investigator's opinion) to comply with all trial requirements.
- 6.1.4 Has had a diagnosis with any disease subtype of MS, by revised 2017 McDonald criteria, for at least 12 months prior to Visit 1 and is expected to remain stable for the duration of the trial.
- 6.1.5 Has an MAS untransformed score of at least 2 in 2 or more of 6 muscle groups (right knee flexors, left knee flexors, right knee extensors, left knee extensors, right plantar flexors, or left plantar flexors) at Visit 1.
- 6.1.6 Currently receiving optimized treatment with at least 1 oral antispasticity drug (baclofen, tizanidine, and/or dantrolene) that has been stable for at least 30 days prior to Visit 1. Despite optimization, the patient does not have adequate relief of spasticity symptoms, including muscle spasms. Optimization of antispasticity medications is defined as having reached the most efficacious and best tolerated dose according to the relevant local prescribing information. The patient must be willing to maintain the same antispasticity medication and not plan to initiate a new course of physiotherapy for the duration of the trial.
- 6.1.7 If currently receiving an approved MS disease-modifying therapy, it must be at a stable dose for at least 3 months prior to Visit 1 and is expected to remain stable for the duration of the trial.

- 6.1.8 If currently receiving dalfampridine or fampridine, it must be at a stable dose for at least 3 months prior to Visit 1 and is expected to remain stable for the duration of the trial.
- 6.1.9 Willing to allow the responsible authorities to be notified of participation in the trial, if mandated by local law.
- 6.1.10 Willing to allow his or her primary care practitioner (if he or she has one) and/or treating neurologist (if he or she has one) to be notified of participation in the trial, if the primary care practitioner/treating neurologist is different from the investigator.

Additional Inclusion Criteria at Randomization (Visit 2)

Patients are eligible for randomization in the trial if, in addition to continuing to meet the Screening (Visit 1) inclusion criteria, they also meet the following criterion prior to Visit 2 (Day 1):

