12.5.3.2 Sensitivity Analysis: Tipping Point

The primary efficacy analysis on secondary endpoint assumes data are either missing at random or missing not at random as per missing data handling strategy described in [Section 12.5.2.1.3](#).

To assess the robustness of the treatment effect with regard to missing data, sensitivity analyses based on a tipping point analysis will be performed for the secondary efficacy endpoint to assess the impact of the missing data assumed MNAR on the secondary estimand.

This analysis will impute missing nabiximols D21 data under a Missing Not at Random approach, using the FAS during the 51-day randomized efficacy period (see [Section 10.1](#)).

Thus, when no penalty is added the tipping point analysis is equivalent to the primary analysis of the secondary endpoint.

This analysis will be conducted using the same approach as the one described for primary efficacy endpoint (see [Section 12.5.2.2](#)). However, as LLMT-4 score is based on 4 muscle groups (and not 6 muscle groups as LLMT-6) as described in [Section 12.5.2.2](#), the Step 5 (Step 2 to Step 4 will be repeated for a plausible ^{nabiximols} value using a grid search method. Firstly larger changes in delta values (delta will range from 0 to 5 by increments of 5/4 where 5/4 represents the maximum effect of an individual MAS transformed score on LLMT-4) will be used. If the inference changes, then smaller changes in delta values (1/4 representing the change of 1 of LLMT-4 score) will be used to identify a more accurate tipping point between the last two delta values which were using larger changes (ie. last delta value with $p < 0.05$ and first delta value with $p \geq 0.05$).

The same tables, figures and listing as those performed for LLMT-6 (as described in [Section 12.5.2.3.3](#)) will be provided for LLMT-4.

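### SAP 10.16: criterion 6.1.5 does not keep the LLMT-4 baseline above zero, and the zero-baseline rule then reports +100% for a patient whose score has not changed

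*SAP*

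**What the plan says.** - Protocol 6.1, criterion 6.1.5: "Has an MAS untransformed score of at least 2 in 2 or more of 6 muscle groups". The list of six ends with "right plantar flexors, or left plantar flexors) at Visit 1", so the two plantar flexors can be the two qualifying groups.
- Protocol 6.1, additional criteria at randomization: patients must meet a diary requirement "in addition to continuing to meet the Screening (Visit 1) inclusion criteria". No knee requirement is added.
- SAP 10.16: "The LLMT-4 defined as the average of the 4 individual MAS transformed scores of knee flexors, knee extensors on both sides of the body". The MAS transformation maps 0 to 0 and 2 to 3.
- SAP 10.16 calculates change and percentage change for each LLMT score. Improvement is a negative percentage (cut-offs from −20% to −50%). The zero-baseline rule begins "Although unlikely to occur as per inclusion criteria 6.1.5, if a baseline LLMT score is equal to 0" and sets the percentage to (x+1) × 100, "where x is the post baseline value".
- SAP 12.5.2.3.3 plans percentage-change summaries, scatterplots against baseline, cumulative distribution plots and a listing for LLMT-6. SAP 12.5.3.2 extends them to LLMT-4: "The same tables, figures and listing as those performed for LLMT-6".

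**The concern.** The SAP relies on one entry criterion to make a zero baseline improbable for all three LLMT scores. That criterion looks at six muscle groups, and LLMT-4 uses only four of them. The two it leaves out are enough to qualify a patient. The special rule can therefore apply to LLMT-4, and when it does it labels a patient with no change as 100% worse.

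LLMT-4 is the only endpoint besides the primary in the hierarchical testing sequence. Its percentage-change tables and plots will be read beside the test, and they would mix real percentages with values produced by the rule.

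**Working it through.** The documents give no figure for how often a zero baseline occurs, so there is none to reproduce. What can be checked is the claim that 6.1.5 guards against one, and what the rule returns.

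**Step 1. Lowest score that 6.1.5 allows.** Assume complete data at the time the criterion is met. Two groups are at untransformed MAS 2 (transformed 3), and all others are at 0.

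| Score | Smallest possible value | Guarded by 6.1.5? |
|---|---|---|
| LLMT-6 | (3 + 3)/6 = 1.0 | yes |
| LLMT-10 | (3 + 3)/10 = 0.6 | yes |
| LLMT-4, both qualifying groups plantar flexors | 0/4 = 0 | no |

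Listing every combination of transformed scores for the six groups gives the same minima. Nine eligible combinations have LLMT-4 = 0: each plantar flexor at 3, 4 or 5 (3 × 3 = 9) with all four knee groups at 0. That shows it is possible; it says nothing about frequency.

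**Step 2. What the rule returns.** The ordinary formula (SAP 10.4) is change divided by baseline, times 100.

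| Baseline | Day 21 | Formula | Percentage change |
|---|---|---|---|
| 0.25 | 0.25 | (0.25 − 0.25)/0.25 × 100 | 0% |
| 0.25 | 0.50 | (0.50 − 0.25)/0.25 × 100 | +100% |
| 0 | 0 | (0 + 1) × 100 | +100% |
| 0 | 0.25 | (0.25 + 1) × 100 | +125% |

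An unchanged zero is indistinguishable from a doubling. If the intention was to add 1 to both baseline and follow-up (my assumption; the SAP does not say so), the result would be ((x+1)/(0+1) − 1) × 100 = 100x. The printed rule is 100 points above that at every x.

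**Step 3. Effect on an arm mean.** Let f be the fraction of patients in an arm with baseline 0 who stay at 0. Compared with scoring them 0%, the mean rises by 100 × f points: +2, +5 and +10 for f = 2%, 5% and 10%. These fractions are assumptions. With the 68 completers in SAP 8.2, 1, 3 or 7 such patients add 100/68 = 1.5, 300/68 = 4.4 or 700/68 = 10.3 points.

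Illustration at f = 10% with the other 90% averaging −10%:
- scored 0%: 0.9 × (−10) + 0.1 × 0 = −9%
- under the rule: 0.9 × (−10) + 0.1 × 100 = +1%

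**Step 4. What uses the percentage.** The LLMT-4 test is on absolute change (SAP 12.5.3.1). Imputation and the tipping point work on scores (SAP 12.5.2.1.6, 12.5.3.2). The responder regression is specified for LLMT-6 (SAP 12.5.2.3.2, Appendix 14). Responder status would not move in any case, since 0% and +100% both fail the −20% cut. That leaves the descriptive LLMT-4 summaries, plots and listings.

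**The case against.** The strongest reply is that this is rare and touches nothing inferential. The SAP says unlikely, not impossible. All scored knee groups must be at MAS 0 in patients with inadequate relief despite optimized treatment, and nothing in the documents shows that this is common. Absolute change appears in the same tables, medians and quartiles are reported with the means, and the planned display of the tested quantity is the LS mean change with its interval (SAP 12.5.4.4). All of this stands, and it limits the weight of the point. It does not make the formula correct or 6.1.5 a safeguard for LLMT-4.

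Three stronger readings are tempting, and the documents do not support them:

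- *Anyone qualifying on plantar flexors alone enters both treatment columns at +100% or more.* Such a patient may have knee groups at MAS 1 or 1+ (transformed 1 or 2), so LLMT-4 can lie anywhere from 0 to 2. The rule needs every scored knee group at 0. Baseline is also set separately for each period, so a zero on Day 1 does not imply one on Day 31.
- *The treatment comparison is distorted.* A patient at 0 at both period baselines adds the same artefact to both arms, and it largely cancels in the difference.
- *Floor patients wrongly dilute the LLMT-4 effect.* They belong to the population of the secondary estimand (SAP Table 9.1-2), the model adjusts for period baseline, and they can still worsen. An analysis restricted to LLMT-4 above 0 would be a preference, not a correction.

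**Conclusion.** The defect is real and small. For LLMT-4, criterion 6.1.5 gives no support to the statement that a zero baseline is unlikely, and the rule returns a wrong value for a zero-baseline patient who stays at 0. The bounds for LLMT-6 and LLMT-10 assume complete data at the time the criterion is met. Because 6.1.5 is worded for Visit 1 while baselines are taken predose on Days 1 and 31, it does not strictly bound the Period 2 baseline of any LLMT score.

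The size depends wholly on f, which the documents do not give. It affects the level of each arm's mean LLMT-4 percentage change, and has little effect on the difference when the baseline is 0 in both periods. No confirmatory result is at risk.

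**What to change.** In SAP 10.16:

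1. Delete the (x+1) × 100 rule.
2. Leave percentage change undefined whenever the period-baseline LLMT score is 0, whatever the post-baseline score. Scoring 0% for those who stay at 0 and nothing for those who rise should be avoided: it would drop only patients who worsened and flatter the means.
3. State that these patients count as not improved in any responder category and remain in all absolute-change analyses.
4. Show the number of zero-baseline patients by treatment arm and period beside the percentage-change outputs.
5. Correct the statement about 6.1.5 so that it no longer covers LLMT-4.

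Leave the confirmatory LLMT-4 analysis unchanged. The cost is a few lines of SAP text and one count in the tables, with no change to eligibility, visits or data collection. The downside is that a few patients will have no percentage value.

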
The primary estimand for this study is defined by the following 4 components:
 
 • Population: Patients with MS, naïve to treatment with nabiximols who have not achieved adequate relief from spasticity with other antispasticity agents but have optimized treatment with at least 1 oral antispasticity drug. • Treatment: • Endpoint: Change in LLMT-6 from Day 1 pre-dose to D21 and from Day 31 pre-dose to Day 51. • Intercurrent events: 
 ○ Treatment-policy: Intercurrent events of non-adherence with IMP, use of prohibited medications, or other protocol deviations will be handled following a 'treatment-policy' strategy. Study data will continue to be collected and analyzed following the occurrence of the intercurrent event, i.e., the measure of effect is regardless of non-compliance, use of prohibited medications, or other protocol deviations. For patients who discontinue IMP, only the period in which this intercurrent event occurs will follow a treatment-policy strategy. Data will continue to be collected and analyzed following the occurrence of the intercurrent event up to the end of the period. ○ Hypothetical strategy: For patients who discontinue IMP during Period 1, their Period 2 data will be assumed to follow a hypothetical strategy, i.e., patients will be assumed to follow a similar pattern of data in Period 2 to those patients in the same Period 2 treatment arm who did not experience this intercurrent event during Period 1. For these patients, Period 2 data will not be collected, and these data will be imputed according to Table 9.1-3. 
Summary Measure: Mean difference in 'change from period level baseline to 21 days of the period assigned to nabiximols' compared to 'change from period level baseline to 21 days of the period assigned to placebo' regardless of treatment compliance and change of other antispasticity medications; following a treatment policy and hypothetical strategy for handling intercurrent events (as described above).

Secondary Estimand

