12.5 Efficacy Analysis

All efficacy analyses, unless otherwise specified will be performed on the FAS during the 51-day randomized efficacy period (as defined in [Section 10.1](#)) regardless of treatment compliance and permanent treatment discontinuation.

To assess robustness of the results with regard to intercurrent events some efficacy analyses may be repeated, for instance:

- During the 51-day on-treatment efficacy period (as defined in [Section 10.1](#)) using only on-treatment assessments (assessments obtained post treatment being set to missing);
- During the 51-days randomized period (as defined in [Section 10.1](#)) using the PP analysis set, If more than 20% of patients from FAS are excluded from the PP Analysis Set;
- During the 51-days randomized period using the Study Completer Analysis Set.
- During the 51-days randomized period excluding patients having at least one efficacy assessment impacted by COVID-19.

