12.5.2.1.1 Missing Data Handling

As stated in [Section 9.1](#), under the hypothetical strategy for handling intercurrent events, Period 2 data will not be collected when patients discontinue IMP during Period 1. In addition, missing data within a single period only may arise if patients decide to withdraw from the study or are lost to follow-up.

For patients who discontinue study before entering Period 2,

- Not collected Period 1 data will be imputed under the missing at random (MAR) assumption if the patient withdraws from the study due to a reason relative to COVID-19 or if the patient is randomized to the placebo/nabiximols treatment sequence and will be imputed under the control-based missing not at random (MNAR) assumption otherwise (i.e., patient lost to follow up or prematurely withdraws from the study and randomized to nabiximols/placebo treatment sequence),
- Not collected Period 2 data will be imputed under the MAR assumption whether or not missing data arise under the hypothetical strategy and whatever the treatment sequence the patient is randomized to.

For patients who discontinue study but enter in Period 2 not collected Period 2 data will be imputed,

- under the MAR assumption if the patient withdraws from study due to a reason relative to COVID-19 and/or is randomized to the placebo/nabiximols treatment sequence,
- under the control-based MNAR assumption otherwise.

Under this framework, for those patients having their missing scores assumed MNAR, their mean profile will be assumed to be the same as those patients in the placebo treatment arm for the period containing the missing data. Details regarding missing data handling are given in [Table 12.5-1](#) below.

Table 12.5-1 Scenarios for Methods of Imputation when Data are not Collected

Scenario	Missing Data	Period 1 Imputation	Period 2 Imputation
1. Data not collected under the hypothetical strategy for handling intercurrent events	Period 2 data not collected due to patients who discontinue IMP or withdraw during Period 1/washout	N/A	Within treatment arm under MAR
2. Missing data arising due to reasons related to COVID-19, (and/or for patients assigned to placebo/nabiximols treatment sequence assignment)	Period 1 post baseline missing data but patient continues in study at least up to Period 2 baseline	Within treatment arm under MAR	Within treatment arm under MAR
	Period 1 withdrawal	Within treatment arm under MAR	Within treatment arm under MAR (Scenario 1)

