12.5.2.3.2 Response Analyses Based on LLMT-6

The reduction from baseline to D21 of respectively $\geq 20\%$, $\geq 30\%$, $\geq 40\%$, $\geq 50\%$ (as described in [Section 10.16](#)) will be analyzed using a logistic regression applied to crossover design using a generalized estimating equation (GEE). The models will be analyzed using the SAS® GLIMMIX procedure with a logit link function and a binary distribution. The marginal log likelihood will be approximated with an adaptive Gauss-Hermite quadrature (obtained using the EMPIRICAL option of the SAS® GLIMMIX procedure) using a likelihood-based sandwich estimator.

The preferred model will include a period level LLMT6 baseline covariate, treatment arm, treatment period, and treatment sequence as fixed effect.

An unstructured covariance will be used to model the residual errors between LLMT-6 scores within the same patient across period. The denominator degrees of freedom will be calculated according to the Kenward-Roger method (e.g. KR2, 2009 version).

This model will provide, for each response analysis, at D21, the estimate of the odds ratios (OR) representing the odds in nabiximols treatment arm versus placebo treatment arm and corresponding 95% CI and nominal p-value. These parameters will be summarized by treatment arm along with number of responders and associated crude response rates.

If less than 5 patients in either treatment arm are considered as responders, only descriptive statistics will be conducted presenting the number and percentage of responders by treatment arm.

In case of non-convergence, appropriate model will be applied.

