Appendix 14 Overview of primary, secondary and exploratory efficacy objectives

Objective Clinical Category	Statistical Category	Estimand/Variable
Primary Objective: To evaluate the effect of multiple doses of nabiximols as adjunctive therapy compared with placebo on a clinical measure of velocity-dependent muscle tone in the lower limbs (Lower Limb Muscle Tone-6; LLMT-6) in patients with multiple sclerosis (MS) who have not achieved adequate relief from spasticity with other antispasticity medications.		
LLMT-6	P1, Primary	Variable: Change from period baseline in LLMT-6 at D21 Population: FAS Regardless permanent treatment discontinuation Regardless premature study discontinuation Regardless major IPD Accounting for COVID-19 impact PLS: Mean difference between nabiximols and placebo Analysis: LSMD from CFB linear mixed-effect model for crossover data adjusted on period baseline LLMT-6 with placebo-based MI under MNAR assumption.
	P1, SA1 (Sensitivity)	Variable: Change from period baseline in LLMT-6 at D21 Population: FAS Regardless permanent treatment discontinuation Regardless premature study discontinuation Regardless major IPD Accounting for COVID-19 impact PLS: Mean difference between nabiximols and placebo Analysis: LSMD from CFB linear mixed-effect model for crossover data adjusted on period baseline LLMT-6 with MI under MNAR assumption. Tipping point analysis
	P1, SUP1 (Supplementary, Subgroup)	Subgroup analyses based on same estimand as primary endpoint
	P1, SUP2 (response analyses)	Variable: proportion of patients with LLMT-6 score reduction criterion cut-offs defined by different percentages of $\geq 20\%$, $\geq 30\%$, $\geq 40\%$, $\geq 50\%$ from period baseline in LLMT-6 at D21 Population: FAS IES: Regardless permanent treatment discontinuation Regardless premature study discontinuation Regardless major IPD Regardless COVID-19 impact PLS: Odd ratio in nabiximols versus placebo Analysis: OR from logistic regression model for crossover data adjusted on period baseline LLMT-6. Single imputation: Missing D21 values are imputed a failure.

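### The LLMT-6 responder failure rule makes no exception for a Period 2 never entered, so crude rates can be lowered by stops on the other treatment and need not match the records behind the odds ratio

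*SAP*

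**What the plan says.** - **Failure rule.** SAP 10.16: "Missing LLMT scores will be considered as not having met any of the improvement criteria (imputed as failure". Appendix 14 (P1, SUP2), with the FAS as population: "Single imputation: Missing D21 values are imputed a failure". Neither makes an exception.
- **Period 2 after a Period 1 stop.** SAP Table 9.1-2, on patients who discontinue IMP in Period 1: "For these patients, Period 2 data will not be collected, and these data will be imputed according to" the imputation rules. Protocol 4.1 agrees: such patients are encouraged to stay only to the end of the period in which they stop. Their Period 1 Day 21 assessment is still wanted.
- **Primary analysis of the same records.** SAP 12.5.2.1.1: "Not collected Period 2 data will be imputed under the MAR assumption whether or not missing data arise under the hypothetical strategy".
- **Responder model.** SAP 12.5.2.3.2: "The preferred model will include a period level LLMT6 baseline covariate", with treatment, period and sequence. On what is reported with the odds ratio: "These parameters will be summarized by treatment arm along with number of responders and associated crude response rates".
- **Records and denominator.** SAP 12.5: "All efficacy analyses, unless otherwise specified will be performed on the FAS during the 51-day randomized efficacy period". However, 12.0 allows percentages on all patients or on patients at risk, 10.1.1 defines the on-treatment Period 2 only for patients exposed in it, and 10.3 and 10.4 need a baseline for change and percentage change.
- **T25FW.** SAP 10.17 and Appendix 14 (E2, SUP1) apply the same failure rule to the exploratory 20% responder analysis.

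**The concern.** Counting a missing value as failure is normally defended because the failure is charged to the treatment the patient was taking. In this crossover the rule does something else for one group. A patient who stops nabiximols in Period 1 has no Period 2 by design. Read literally, the rule makes that patient a placebo non-responder without any placebo, while Period 1 can still be scored as a nabiximols response. Placebo stops do the reverse. If stopping differs between treatments, part of that difference appears in the response rate of the wrong treatment.

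There is also a mismatch of records. A never-entered Period 2 has no period baseline, and neither 12.5.2.3.2 nor Appendix 14 supplies one; the imputed Period 2 baseline in 12.5.2.1.5 belongs to the primary analysis. The records would then count in a FAS-based rate but not in the odds ratio beside it. Two programmers could follow the SAP and produce different tables.

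**Working it through.** **The plan's own figures.** The documents give no figure for the responder analysis. The sample size reproduces and is not affected: a paired t-test with n = 46, difference 0.30, SD 0.71 and two-sided 5% has 80.07% power; 46/0.90 = 51.1, rounded up to 52; 68 completers at SD 0.71 give 92.98%, in line with SAP 8.2.

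**Inputs.** Equal sequences follow from 1:1 allocation. All else is assumed: response p = 0.30 on both treatments (no true effect); dN and dP, the shares stopping on nabiximols and placebo, the same in both periods and independent of response; s, the share of stoppers still assessed at Day 21.

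**Formulae.** Half of each treatment's periods fall in Period 2, and those are lost to stops on the other treatment.

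- Literal rule, FAS denominator: nabiximols p(1 − dN(1 − s))(1 − dP/2); placebo p(1 − dP(1 − s))(1 − dN/2).
- Never-entered periods left out: nabiximols p(1 − dN(1 − s)); placebo p(1 − dP(1 − s)).

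**Effect of the never-entered periods alone** (s = 1):

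| dN/dP | nabiximols | placebo | OR multiplier |
|---|---|---|---|
| 10%/2% | 29.70% | 28.50% | 1.060 |
| 15%/3% | 29.55% | 27.75% | 1.092 |
| 20%/5% | 29.25% | 27.00% | 1.118 |
| 9%/9% | 28.65% | 28.65% | 1.000 |

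To three decimals the multiplier is the same at s = 0.5 and s = 0.

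**Scaled to the planned loss.** The 10% in Protocol 13.1 is loss over the whole trial. Non-completion, averaged over sequences, is [dN + (1 − dN)dP(1 − s) + dP + (1 − dP)dN(1 − s)]/2. At 15%/3% this is 9.0%, 13.3% and 17.5% for s = 1, 0.5 and 0. Solving for exactly 10% gives, for the same three values of s:

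- 5:1 split: 1.103, 1.068, 1.050
- 2:1 split: 1.050, 1.034, 1.025
- 1:1 split: 1.000 throughout

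**Net crude OR at 15%/3%, true value 1.00** (s = 1, 0.5, 0):

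- literal rule: 1.092, 1.000, 0.911
- never-entered periods left out: 1.000, 0.916, 0.834

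The values below 1.00 in the second line come from counting a missing Day 21 in an entered period as failure. That is a separate feature of the endpoint.

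**Against sampling error.** 68/0.90 is about 76 patients, 38 per sequence (assumed). The SE of the log OR is √(2(1 − ρ)/(76 × 0.21)) = 0.354 at ρ = 0 and 0.250 at an assumed ρ = 0.5. ln(1.092) = 0.088, or 0.25 to 0.35 of one SE.

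**Mismatch of records.** At 15%/3%, 38 × 0.15 = 5.7 placebo and 38 × 0.03 = 1.1 nabiximols periods would be failures without exposure. A FAS rate would use 76 periods per treatment; the model would use about 70.3 and 74.9.

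**The case against.** The strongest reply is that these records may do no harm to any inference. Without a period baseline they leave the model, so the odds ratio, its interval and the nominal p-value would not contain them. Sections 10.1.1, 10.3 and 10.4 could be read as removing them from the crude rates too. What is left is a descriptive rate and an unclear denominator. Most of this stands. It does not settle the matter, because 10.16 and Appendix 14 act on any missing score in the FAS and nothing says which rule prevails.

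A second reply is that no net bias in one direction is shown. This also stands: under no effect the literal rule gives exactly 1.00 when half the stoppers are assessed, and 0.91, against nabiximols, when none are.

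A third is that failure imputation is a deliberate, conservative choice, and a supplementary analysis may handle missing data differently from the primary. That holds for periods the patient entered. It does not cover a never-entered period, where the failure is not charged to the treatment taken.

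Finally, the size rests on assumed rates, and the 15%/3% case exceeds the planned 10% loss in two of its three variants. That is correct, which is why the rescaled figures are shown.

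**Conclusion.** The point holds as a minor one. As written, the failure rule covers a Period 2 that was never meant to be collected. If the FAS is the denominator, it lowers each treatment's crude response rate by stops on the other treatment. The crude rates and the odds ratio then most likely rest on different records. The never-entered periods multiply the crude odds ratio by 1.06 to 1.12 at the unequal rates tried, by about 1.02 to 1.10 when scaled to 10% loss with 2:1 to 5:1 splits, and by 1.00 at equal stopping. This assumes 30% response, equal sequences and stopping independent of response.

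A reader might infer more, and the documents do not support it:

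- **That the model odds ratio is distorted.** This would need a Period 2 baseline for these records, and nothing in the responder section supplies one.
- **That the responder analysis favours nabiximols.** No stopping rates by arm are given, and the net direction changes with the share of stoppers assessed at Day 21.
- **That the trial's conclusions are at risk.** The analysis is supplementary with nominal p-values and outside the testing hierarchy. The primary and LLMT-4 tests do not use this rule, and the T25FW version is exploratory.

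**What to change.** In SAP 10.16, 10.17, 12.5.2.3.2 and Appendix 14 (P1 SUP2 and E2 SUP1):

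1. Restrict the failure rule to a missing Day 21 in a period the patient entered, where it is charged to the treatment taken.
2. State that a never-entered Period 2 is not scored as failure and is left out of both the crude rates and the model.
3. State one set of records and one denominator for the rates and the odds ratio.

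The cost is a few sentences and slightly fewer records in the crude table. The odds ratio remains a composite in which a missing Day 21 in an entered period is a failure. The change therefore removes the wrong attribution but does not make the odds ratio unbiased for response when many stoppers go unassessed.

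Optionally, for LLMT-6, add a sensitivity analysis that takes responder status from the 300 completed datasets of the primary analysis and combines the fits with Rubin's rules. That is 4 thresholds × 300 = 1,200 logistic fits. The minimum of five responders and the rule "In case of non-convergence, appropriate model will be applied" would need defining across imputations. Responder status is only approximate there, because imputed scores are continuous and truncated at 0 and 5. It should not replace the main responder analysis without discussion, since it also removes the failure rule for entered periods: under 12.5.2.1.1, Period 2 withdrawals on nabiximols would be imputed as missing at random.
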